5.4.4 Liver enzyme and bilirubin elevations

The analysis of liver enzyme and bilirubin elevation will be done separately for each period (double-blind period, nintedanib exposure period, over the whole trial).

Liver enzyme and bilirubin elevations will be reported using the following definitions:

- (ALT and/or AST ≥ 3 fold ULN) and bilirubin ≥ 2 fold ULN ^[1]
- ALT ≥ 5 fold ULN and/or AST ≥ 5 fold ULN
- ALT ≥ 3 fold ULN and/or AST ≥ 3 fold ULN

^[1] within a time window of 30 days i.e. the elevation of bilirubin should appear within 30 days after the elevation of AST and/or ALT

The proportion of patients presenting signs of hepatic injury will be summarised, based on the following definition for signs of hepatic injury:

- ALT and/or AST ≥ 8 fold ULN
- ALT and/or AST ≥ 3 fold ULN and total bilirubin ≥ 2 fold ULN ^[2]

- ALT and/or AST ≥ 3 fold ULN and unexplained INR > 1.5 ^[2]
- ALT and/or AST ≥ 3 fold ULN and unexplained eosinophilia ($> 5\%$) ^[2]
- ALT and/or AST ≥ 3 fold ULN and appearance of fatigue, nausea, vomiting, right upper abdominal quadrant pain or tenderness, fever and/or rash within ± 7 days of the abnormal ALT and/or AST laboratory test result (please refer to [Table 9.4: 1](#) for the list of relevant MedDRA preferred terms to support the derivation of a potential hepatic injury)

^[2] in the same blood draw sample

In addition, maximum individual elevations based on worst value on treatment will be defined as:

- ≥ 3 fold ULN; ≥ 5 fold ULN; ≥ 8 fold ULN for AST and ALT and AST and/or ALT
- ≥ 1.5 fold ULN; ≥ 2 fold ULN for Bilirubin
- $\geq 1.5 \times \text{ULN}$; ≥ 2 fold ULN for alkaline phosphatase (ALK)
- $\geq 3 \times \text{ULN}$ for Gamma-Glutamyl-Transferase (GGT)

Note: ULN refers to the Upper Limit of Normal from the central or local laboratory analysing samples.

5.4.4.1 Time-to-event analyses for liver enzyme elevations

- Time to liver enzyme and bilirubin elevation (ALT and/or AST $\geq 3 \times \text{ULN}$ and bilirubin $\geq 2 \times \text{ULN}$)
- Time to liver enzyme elevation (ALT and/or AST $\geq 5 \times \text{ULN}$)
- Time to liver enzyme elevation (ALT and/or AST $\geq 3 \times \text{ULN}$)

Time to first occurrence of the above described liver enzyme elevations [days] will be analyzed as

$$\text{Date of event/censoring} - \text{Date of first treatment intake} + 1 \text{ day.}$$

Patients with no such event occurred during the respective period will be censored according to the mechanism for censoring as described in [Table 5.4.4.1: 1](#).

Table 5.4.4.1: 1 Censoring rules for time to first occurrence of liver enzyme elevations

Rule	Situation	Outcome	Date of event/censoring
1	Patient had a documented event during treatment or REP ^[1] of respective period	Event	Earliest date of event
2	Patient had no documented event during treatment or REP ^[1] of respective period.	Censored	Earliest date of 
 • end date of REP of respective period, • date of last contact when patient was known to be alive and event free, • date of death.

^[1] See [Sec. 6.1](#) for definition of Residual Effect Period (REP)

These times to onset of first event will also be summarized in categories:

- Double-blind period:
 - ≤2 weeks (14 days)
 - >2 to ≤6 weeks (42 days)
 - >6 to ≤12 weeks (84 days)
 - >12 to ≤18 weeks (126 days)
 - >18 to ≤24 weeks (168 days)
 - >24 weeks (168 days)
 - Censored

- Nintedanib exposure period, over the whole trial:
 - ≤2 weeks (14 days)
 - >2 to ≤6 weeks (42 days)
 - >6 to ≤12 weeks (84 days)
 - >12 to ≤24 weeks (168 days)
 - >24 to ≤36 weeks (252 days)
 - >36 to ≤52 weeks (364 days)
 - >52 to ≤64 weeks (448 days)
 - >64 to ≤76 weeks (532 days)
 - >76 weeks (532 days)
 - Censored

Further categories might be defined if needed.

5.4.5 Vital signs

Weight minimum relative change from baseline will be summarized as continuous variable and in categories:

- Relative decrease of more than 10% (excl.)
- Relative decrease of between 5% (excl.) and 10% (incl.)
- Relative decrease of between 0% (excl.) and 5% (incl.)
- Relative increase (≥0%)

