Results from the IPF and SSc-ILD programme in adults show nintedanib to be associated with statistically significant and clinically meaningful slowing of the progressive decline in lung function as measured by FVC over 1 year.

In the phase III study performed to investigate the efficacy and safety of nintedanib in subjects with non-IPF chronic fibrosing ILDs that were progressive despite management deemed appropriate in clinical practice (Trial 1199.247, INBUILD[®]) [[P17-10582](#)], nintedanib significantly reduced the progression of fibrosing ILD, as measured by the annual rate of decline in forced vital capacity (FVC) over 52 weeks compared with placebo in both in the overall population and in the co-primary population of subjects with a usual interstitial pneumonia (UIP)-like fibrotic pattern on HRCT. Compared with placebo, relative reductions of the annual rate of decline in FVC over 52 weeks of 57% in the overall population, 61% in patients with HRCT with UIP-like fibrotic pattern was observed. Consistent results were obtained in the complementary population of patients with HRCT with other fibrotic patterns [[P19-08802](#)]. Although the INBUILD[®] trial was not powered to study individual ILDs, subgroup analyses suggested that nintedanib had a consistent effect on FVC decline across diagnostic groups. The effect of nintedanib versus placebo on reducing the rate of FVC decline (mL/year) was consistent across subgroups by ILD diagnosis in the overall population [[P20-02333](#)].

The most commonly reported AEs were gastrointestinal disorders. Of those, the most frequent events were diarrhoea, nausea, and vomiting. Most of these events were of mild or moderate intensity, reported as non-serious, and were managed by symptomatic treatment and/or temporary interruption and/or reduction of the nintedanib dose. Diarrhoea, nausea, vomiting, which may lead to dehydration and/or electrolyte disturbances, and abdominal pain are considered adverse reactions of nintedanib treatment in adults. More patients in the nintedanib group than in the placebo group reported weight and appetite decrease as AEs. Weight decreased and appetite decrease are considered adverse drug reactions of nintedanib treatment.

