4.1.2 Selection of doses in the trial and dose modifications

In order to match the systemic exposure reached in adult IPF patients, the nintedanib doses in paediatric patients were predicted based on body weight dependent allometric scaling (scaling of adult clearance using an exponent of 0.75, consistent with the exponent estimated in population pharmacokinetics [PopPK] analyses in adults; refer to the current version of the Investigator's Brochure Nintedanib in Idiopathic Pulmonary Fibrosis, Systemic Sclerosis and Progressive Fibrosing Interstitial Lung Disease [[c01783972-16](#)] for details). This approach is considered acceptable, assuming a minor role of developmental changes referring to nintedanib PK for the selected target population. A population mean nintedanib exposure of 80% to 125% compared to adult IPF patients treated with 150 mg b.i.d. was targeted for the determination of the planned doses by body weight bin in the paediatric population as provided in [Table 4.1.2: 1](#).

The patient's weight will be measured at screening, at randomization and at each IMP dispensing visit thereafter (see [Flow Chart](#) for details). At randomization the dose assigned will be based on the patient's weight at baseline (Visit 2). At subsequent visits the dose will be adjusted for any changes of the patient's weight resulting in a change of the body weight bin. IRT will assign the proper dose based on the patient's weight recorded at the respective visit.

Table 4.1.2: 1 Dose assignment and dose reduction possibilities based on body weight bins according to ICH E11

| Body weight bin | Weight range | Dose (b.i.d.) | Capsule strengths | Dose reduction possibility (b.i.d.) | Capsule strengths |
|-----------------|-------------------|---------------|---------------------------|-------------------------------------|---------------------------|
| 1 | 13.5* to <23.0 kg | 50 mg | 25 mg (2x) | 25 mg | 25 mg (1x) |
| 2 | 23.0 to <33.5 kg | 75 mg | 25 mg (3x) | 50 mg | 25 mg (2x) |
| 3 | 33.5 to <57.5 kg | 100 mg | 100 mg (1x) or 25 mg (4x) | 75 mg | 25 mg (3x) |
| 4 | ≥57.5 kg | 150 mg | 150 mg (1x) or 25 mg (6x) | 100 mg | 100 mg (1x) or 25 mg (4x) |

* Patients <13.5 kg of weight are excluded from the trial

Based on population anthropometric measures of weight by age, most children younger than 10 are expected to fall into body weight bin 1–2, younger adolescents in bin 3 and older ones in bin 4.

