5.2.1.1 Body weight

Measurement of body weight will be performed at the time points specified in the [Flow Chart](#). If possible, the patient's weight in the 2 years before screening (Visit 1) will be recorded, in order to detect any potential change in growth velocity over time.

Body weight measurements will be recorded in the source documents and transcribed into the CRF.

These measurements will be used to assess safety, and to assign the proper dose of trial medication at randomisation and subsequent IMP dispensing visits.

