- The pre-dose PK sample will be taken immediately before drug administration, study medication will be administered, and post-dose PK samples will be taken at timepoints defined (see [Flow Chart for PK blood sampling](#) for details). Date and exact clock time of drug administration and blood sampling must be recorded in the eCRF.
- After administration of trial medication, the patient's acceptability questionnaire will be administered (Visit 3 only).
- Compliance will be checked and drug accountability will be completed (Visit 3 only; at Visit 7 drug accountability is to be completed only in case of dose reduction / increase).
- Adverse events, any ILD exacerbations, respiratory-related hospitalizations [REDACTED], and concomitant therapy since last visit will be reviewed and recorded.
- Physical examination including vital signs and weight (the latter Visit 3 only) will be performed; data will be recorded in source documents and transferred as instructed.
- SpO₂ measurement will be conducted on room air at rest.
- FVC measurement will be conducted according to procedures defined (see ISF for details).
- Blood and urine samples (safety laboratory tests, and pregnancy test on serum in female patients only) will be collected and submitted to the central laboratory.

- New medication wallets will be assigned by using the IRT system and dispensed, returned wallets will be collected as instructed (see ISF for details) (Visit 3 only).
- The next visit will be scheduled; patient and parent(s)/legal guardian will be instructed on procedures to be followed until the next visit.

Visits 4, 5, 6, 8, 9, X (treatment period)

Observations and procedures:

- PedsQL™ questionnaire will be administered prior to any other procedures and checked for completeness (Visit 6 and Visit 9 only).
- Compliance will be checked and drug accountability will be completed.
- Criteria for dose reduction / interruption will be checked, if any.

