6.7 BASELINE, TIME WINDOWS AND CALCULATED VISITS

As a general rule, the last assessment/measurement observed prior to start of trial medication will be used as baseline. If the time of the assessment/measurement was not captured, and it was on the same day trial medication started, it will be assumed that it was taken prior to the intake of trial medication. For the nintedanib-exposure period, the last measurement prior to the first nintedanib intake was defined as the baseline measurement.

Visit windowing will be performed as described in the following tables, in order to assign data to the relevant study visit based on the actual day of the assessment. Data will be analyzed using the re-calculated visits in the statistical tables. However, in the listings, all visits performed will be displayed (even if outside time-window), along with the re-calculated visit.

Exception:

to account for the short timespan between planned visit 6 (with first open-label intake) and visit 7, a special rule is applied to analyses by visit (not cumulative across visits) in case assignment to visit windows leads to missing values at visit 6 or subsequent visit to take possible multiple measurements in the respective other time window into account.

If such an assessment lies in analysis visit window of visit 7, but not later than 1 month after the planned day of visit 7 and still within the double-blind period, then it is allocated to the analysis visit 6.

Similarly, if such an assessment lies in analysis visit window of visit 6, but after the planned day of visit 6 and not within the double-blind period, then it is allocated to the subsequent visit where this assessment is planned.

If after windowing of visits at baseline, two or more values fall within the same baseline interval, then the last value prior to first drug intake will be taken into account. If after windowing of post-baseline visits, two visits fall in the same interval, then the measurement closest to the planned visit will be taken into account. If only on-treatment values are to be considered, this rule will be applied to on-treatment assessments only. In case two measurements are equidistant from the planned visit, then the last one will be picked.

Table 6.7: 1 Time windowing rules for FVC, SpO₂, missed school days, vital signs (syst. and diast. blood pressure, pulse rate) and laboratory tests (incl. LDH)

Time window of actual day ^[1,2]			Allocated to		

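### The planned weight statistic, a minimum unadjusted percentage change from baseline, cannot tell stalled weight gain from normal growth in patients aged 6 to 17

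*SAP*

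**What the plan says.** Protocol 1.2 treats weight loss as an established effect in adults: "Weight decreased and appetite decrease are considered adverse drug reactions of nintedanib treatment". For decreased appetite, Protocol Table 1.4.2:1 names a weight check every 12 weeks and safety committee monitoring as mitigation.

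On measurement, Protocol 4.1.2 says the patient's "weight will be measured at screening, at randomization and at each IMP dispensing visit thereafter". The first post-baseline value is at week 2, since Protocol 6.2.2 states for Visits 3 and 7: "Physical examination including vital signs and weight (the latter Visit 3 only) will be performed". With the flow chart, this gives weeks 0, 2, 6, 12, 24, 36 and 52, then every 12 weeks. Protocol 5.2.1.1 also collects weights from the two years before screening, "in order to detect any potential change in growth velocity over time".

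On analysis, SAP 5.4.5 states: "Weight minimum relative change from baseline will be summarized as continuous variable and in categories". The mildest loss band is "Relative decrease of between 0% (excl.) and 5% (incl".) and the top band is "Relative increase (≥0"%). SAP 5.4.5 does not say over which period the minimum is taken. Under SAP 6.7, "the last assessment/measurement observed prior to start of trial medication will be used as baseline", with a separate baseline before the first nintedanib intake for the nintedanib exposure period. SAP Table 6.7: 2 gives weight its own visit windows. SAP 7.8.3 promises descriptive statistics for vital signs without naming them. The pre-study weights reappear in the visible SAP only as a baseline description (5.4.1.1).

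**The concern.** A minimum change suits adults, whose expected change is about zero. Patients here are 6 to 17 years old, and the dosing bins in Protocol Table 4.1.2: 1 presume that weight rises with age. In a child, harm can appear as gain that slows or stops while weight is still above baseline. A minimum looks backwards: once a child has grown past the early values, later visits matter only if weight falls below those values again.

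At stake is the long-term weight record. All patients receive nintedanib after week 24, so from then on no concurrent control separates a drug effect from growth, and Protocol 3.2 relies on that phase for longer-term safety. A table of minimum changes could look the same whether or not the children kept growing.

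**Working it through.** The plan gives no figure for this analysis, so there is nothing to reproduce. The check applies the SAP 5.4.5 rule to weight paths at the scheduled visits.

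**Inputs from the documents.** The bands (SAP 5.4.5), the baseline rule (SAP 6.7) and weight at weeks 2, 6, 12, 24, 36, 52, 64 and 76.

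**Assumptions, not in the documents.** Gain of 8% a year, range 5 to 11.4%; independent within-child measurement SD of 0.5, 1 or 2%. For scale, crossing bin 3 (33.5 to 57.5 kg) in an assumed 5 to 7 years implies (57.5/33.5)^(1/5) − 1 = 11.4% to (57.5/33.5)^(1/7) − 1 = 8.0% a year.

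**Step 1: no measurement error.** Change at week t = 100 × [(1 + g)^(t/52) − 1].

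| Path | Change (%) at weeks 2, 6, 12, 24, 36, 52, 64, 76 | Minimum | Band |
|---|---|---|---|
| 8% a year throughout | 0.30, 0.89, 1.79, 3.62, 5.47, 8.00, 9.94, 11.91 | +0.30 (week 2) | increase |
| Flat from baseline | 0 at all visits | 0 | increase |
| Gain to week 24, then loss | 0.30, 0.89, 1.79, 3.62, 2.18, 0.35, 0.35, 0.35 | +0.30 (week 2) | increase |
| Dip at week 12 | 0.5, 0.5, −3.0, then 0.5 | −3.0 (week 12) | 0 to 5% decrease |

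The third child loses 100.35/103.62 − 1 = −3.2% from the peak, and the minimum does not move. The fourth child's loss goes below the early values and is captured.

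**Step 2: with measurement error** (200,000 simulated children per scenario, visits to week 76; SD 0.5 / 1 / 2%).

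| True path | Increase band (%) | Any decrease band (%) |
|---|---|---|
| 8% a year throughout | 63 / 48 / 37 | 37 / 52 / 63 |
| 8% a year to week 24, then no gain | 63 / 48 / 34 | 37 / 52 / 66 |
| Flat from baseline | 11 / 11 / 11 | 89 / 89 / 89 |

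The last row has a closed form. With no true change, baseline and k later values are exchangeable, so the chance that baseline is the lowest is 1/(k + 1): 1/5 = 20% for the four visits to week 24, and 1/9 = 11% for the eight visits to week 76. With 8% gain a year, the minimum falls at week 2 in 79 / 61 / 46% of children.

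**Step 3: what a growth-adjusted measure would show.** A flat child's shortfall against expected weight is 1/(1 + g)^(t/52) − 1.

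| Expected gain a year | Week 24 | Week 52 | Week 76 |
|---|---|---|---|
| 5% | −2.2% | −4.8% | −6.9% |
| 8% | −3.5% | −7.4% | −10.6% |
| 11.4% | −4.9% | −10.2% | −14.6% |

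The child who stops at week 24 is 1.08^(24/52)/1.08^(76/52) − 1 = 1/1.08 − 1 = −7.4% against expected weight at week 76. The bands show nothing of this.

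**Step 4: minimum against by-visit change.** To separate 10% from 0% gain a year (between-child SD 3%, measurement SD s of 1 to 2%, six visits to week 52), the minimum has an AUC of 0.72 to 0.79 and the raw week-52 change 0.95 to 0.98. The latter agrees with Φ{ln 1.1/√[2(0.03² + 2s²)]}: Φ(0.0953/0.0469) = 0.98 for s = 1%, and Φ(0.0953/0.0583) = 0.95 for s = 2%.

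**The case against.** The strongest reply is that the bands count what the protocol names as the adverse reaction, weight decrease, including losses above 5% and above 10%, and that other outputs cover the rest. The windows in SAP Table 6.7: 2 make sense only if by-visit summaries are intended. Protocol 7.2.5 has safety-relevant data assessed for change from before treatment. Clinically relevant changes become adverse events and are tabulated, and the safety committee reviews safety data regularly. Height, sitting height and leg length have their own secondary endpoint. Part A allows a placebo comparison of raw change. Everything is descriptive, with about 20 against 10 patients.

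Much of this stands, and it rules out three stronger readings that a reader might infer:

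- **That the minimum is fixed at the earliest visit.** It is not; a fall below the early value moves it.
- **That a child who stops gaining is labelled an increase.** This is exact only without measurement error or for a plateau clearly above baseline. With error, a child flat from baseline is recorded as a decrease in about 89% of cases over eight visits. The difficulty is that 37 to 63% of normally growing children are recorded as a decrease too.
- **That this is the only weight analysis, or that a standardised one is absent.** The by-visit windows contradict the first. On the second, the further-endpoint text of the SAP is not visible. Its references include the LMS method and a WHO growth page; the page named is height-for-age, so a weight or BMI z-score can be neither confirmed nor excluded.

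What the reply does not supply is any visible analysis that adjusts weight for growth, or any use of the pre-study weights for their stated purpose. Adverse event reporting depends on the investigator's judgement of relevance, and committee review is monitoring rather than planned reporting. Step 4 does show that raw by-visit change would recover much of the lost information, so stating it explicitly is the first part of the remedy. Standardisation is then needed because expected gain varies with age and sex, and no control remains after week 24.

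**Conclusion.** The point holds in a limited form. The SAP 5.4.5 statistic captures true loss below the early values. It does not usefully separate gain that stalls later, or loss after a period of gain, from normal growth, and it calls zero change an increase. Under the assumed growth and error, the share in the increase band by week 76 differs by 0 to 3 percentage points between a child who stops gaining at week 24 and one who does not.

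The growth rates and measurement SDs are assumptions, and the percentages move with them. The structural result does not: a minimum cannot respond to changes that stay above it. The conclusion concerns the visible text only and lapses if unpublished SAP sections already plan a standardised weight measure. It is a worthwhile correction to safety reporting; it does not affect the primary endpoints.

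**What to change.** Unless an unpublished section already does so, state in SAP 5.4.5 and 7.8.3 that:

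- change from baseline in weight is summarised at each windowed visit (Table 6.7: 2) and by analysis period, both raw and as a measure standardised for age and sex, for example a BMI-for-age z-score by the LMS method, with the reference for older adolescents named in advance;
- the number of children whose z-score falls by a pre-stated amount is reported, as a reporting threshold and not a treatment rule;
- the pre-study weights are shown as context for each child's earlier growth;
- the current bands stay as a supplementary table, with the period stated and the last band renamed as no decrease.

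Weight, height, age and sex are already collected. The cost is one derived variable, one more table and the choice of growth reference, which matters because at least 20 of the 30 or more patients are to be adolescents.

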6. GENERAL ANALYSIS DEFINITIONS

6.1 TREATMENT(S)

For treatment specifications, please refer to CTP Section 4.

The following trial periods will be defined: screening, post-randomization, blinded treatment period (with sub-periods treatment period, off-treatment, residual effect period and follow-up), open-label treatment period (with sub-periods treatment period, off-treatment, residual effect period and follow-up), nintedanib exposure period (with sub-periods treatment period, off-treatment, residual effect period and follow-up), and post-study as follows (Note: As described below, the last day of each of the following periods is excluded from the respective period. It defines the first day of the subsequent period):

- Screening: from informed consent to randomization
- Post-randomization (optional^[a]): from randomization to first randomized trial drug intake in blinded treatment period
- Double-blind period:
 - Blinded treatment period: from first randomized trial drug intake (or re-start of treatment if interruption) to last blinded trial drug intake (or the day before start date of interruption, if interruption) plus one day
 - Blinded off-treatment (optional^[a]): from start date of interruption to re-start of blinded treatment
 - Residual Effect Period: the Residual Effect Period (REP) of nintedanib for the pediatric program is 28 days. This is the period from the last blinded trial drug intake plus one day to last blinded trial drug intake plus 28 days plus one day or the day of first open-label treatment administration (whichever occurs earlier)
 - Blinded follow-up (optional^[a]): from last blinded trial drug intake plus 29 days up to the beginning of post-study period. This period is only created if last blinded trial drug intake took place more than 28 days before trial completion, or for patients having prematurely discontinued the blinded treatment and still continuing the trial
- Nintedanib exposure period:
 - Nintedanib treatment period: from first nintedanib intake (or re-start of treatment if interruption) to last nintedanib intake (or the day before start date of interruption, if interruption) plus one day
 - Nintedanib off-treatment (optional^[a]): from start date of interruption to re-start of nintedanib treatment
 - Nintedanib residual effect period: from the last nintedanib intake plus one day to last nintedanib intake plus 28 days plus one day
 - Nintedanib follow-up (optional^[a]): from last nintedanib intake plus 29 days up to the beginning of post-study period. This period is only created if last trial drug intake took place more than 28 days before trial completion, or for

patients having prematurely discontinued the treatment and still continuing the trial

- Over the whole trial:
 - Whole trial treatment period: from first randomized trial drug intake (or re-start of treatment if interruption) to last study drug intake (or the day before start date of interruption, if interruption) plus one day
 - Whole trial off-treatment (optional^[a]): from start date of interruption to re-start of treatment
 - Whole trial residual effect period: from the last trial drug intake plus one day to last trial drug intake plus 28 days plus one day
 - Whole trial follow-up (optional^[a]): from last trial drug intake plus 29 days up to the beginning of post-study period. This period is only created if last trial drug intake took place more than 28 days before trial completion, or for patients having prematurely discontinued the treatment and still continuing the trial

- Open-label period:
 - Open-label treatment period: from first open-label nintedanib intake (or re-start of treatment if interruption) to last open-label nintedanib intake (or the day before start date of interruption, if interruption) plus one day
 - Open-label off-treatment (optional^[a]): from start date of interruption to re-start of open-label treatment
 - Open-label residual effect period: from the last open-label trial drug intake plus one day to last open-label trial drug intake plus 28 days plus one day
 - Open-label follow-up (optional^[a]): from last open-label trial drug intake plus 29 days up to the beginning of post-study period. This period is only created if last open-label trial drug intake took place more than 28 days before trial completion, or for patients having prematurely discontinued the open-label treatment and still continuing the trial

- Post-study period: from the latest of
 - last trial drug intake plus 29 days
 - end of study participation date (from the End of Study page of the eCRF)
 - follow-up visit
 - early end of treatment visit plus 1 day .

This period is not created if date of first trial drug intake in extension trial is before last trial drug intake plus 28 days.

^[a] This period is optional insofar as it does not necessarily exist for all patients.

Assessments on day of first open-label intake will be handled as follows:

- Assessments with time record: period is assigned based on time stamp (if time lies prior to open-label start then double-blind period; otherwise, open-label period)
- Assessments without time record: assigned to double-blind period, even if interruption prior to open-label start (if interruption longer than REP, then assessment falls into double-blind follow up period and thus, will not be evaluated anymore).
- Exception: AEs and concomitant medications with start date on day of open-label start will be assigned to the open-label period.

Further details will be specified in the ADS plan.

If in the double-blind period an interruption is not followed by a re-start of blinded treatment then this is counted as (early) discontinuation of the blinded treatment period. Over the whole trial, this will be counted as whole trial off-treatment period.

For safety analyses, data up to the end of the double-blind residual effect period / whole trial residual effect period / nintedanib residual effect period will be considered on-treatment.

For on-treatment efficacy analyses, data up to the day after last trial drug intake (included) will be considered.

